### **Study Protocol I- Thoracoscopy (Treatment Arm)**

Patients will undergo medical thoracoscopy (rigid or semi-rigid) within 48 hours of randomization. A single port (with a maximum of 2 ports) will be placed and thoracoscopy will be performed under monitoring as per standard protocols, with the patient in a lateral decubitus position. The pleura will be carefully inspected through the thoracoscope under direct visualization. Adhesiolysis will be attempted and pleural irrigation will be done. At the end of the procedure, a drain will be inserted and connected to an underwater seal with a negative pressure suction. As per standard of care, a chest CT without contrast will be performed when chest tube drainage is < 75 mLs and if there was no evidence of significant pleural effusion (<200 ml), the catheter will be removed. The fluid volume will be calculated by measuring the maximum perpendicular distance between the surface and the chest wall right above the diaphragm with at maximum inspiration in the most dependent position. Any need for additional drainage or administration of fibrinolytic or surgery will be considered treatment failure.

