### **II-Fibrinolytic Therapy (Control Arm)**

A chest tube (14-French or less) will be inserted under ultrasonography into the most dependent area of the pleural effusion or into the largest loculation in patients with multi-loculated effusions. The dose of DNase (Pulmozyme, Genentech, USA) will be 5 mg and the dose of tPA (Actilyse, Genentech, USA) will be 10 mg, each in 50 ml of 0.9% NaCl. The tPA and DNase will not be mixed together in one syringe. Concurrent tPA and DNase will be administered intrapleurally through the chest tube followed by saline flush. The tube will then be clamped for 120 minutes and after which it will be connected back to wall suction. The intrapleural therapy will be given twice daily for a maximum of 6 doses. As per standard of care, a chest CT without contrast will be performed when chest tube drainage is < 75 mLs and if there was no evidence of significant

pleural effusion (<200 ml), the catheter will be removed . Any need for additional drainage or more doses of fibrinolytic from the existing drainage over and above the 6 doses mentioned or surgery will be considered treatment failure.

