### **Secondary outcome measures:**

- Number of days with chest tube drainage
- Total length of hospital stay
- Failure rate of assigned treatment necessitating intervention defined as any of the following:
  - 1-Surgical intervention (VATS, open thoracotomy) in either arm
  - 2-Need of additional chest tube and/or fibrinolytic therapy in the medical thoracoscopy arm due to clinical non-responsiveness
  - 3-Need of additional chest tube in the fibrinolytic therapy arm due to clinical non-responsiveness
- Adverse events
  - Pleural bleeding defined as drop in serum hematocrit requiring blood transfusion or causing hemodynamic instability
  - Significant pain requiring escalation of analgesia
- In-hospital and 30-day mortality
- Change in pleural fluid volume on chest CT scan from randomization (day 0) to prior to chest tube removal measured by radiologist ([name]) blinded to treatment allocation using image J software. Volume of pleural effusion will be obtained by examination of radiographic images obtained during the standard-of-care CT examination.
- Infectious biomarker (CRP) from randomization (day 0), at removal of chest tube and 12 weeks as per standard of care
- Total costs of each treatment modality in each treatment site

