## **Sample Size and Statistical Analysis**

The difference in length of post-intervention hospital stay of 2 days between the two treatment arms would be clinically important.

This rationale was based on previous large VATS case series reported by Luh and colleagues in which the mean postoperative stay was  $7.2 \text{ d} \pm 3.2 \text{ d}$  versus  $11.8 \text{ d} \pm 9.4 \text{ d}$  from randomization to fibrinolytic therapy until discharge in the MIST2 trial and  $10 \text{ d} \pm 1.8 \text{ d}$  from first intrapleural treatment dose until discharge reported by Piccolo and colleagues.

To demonstrate this difference with 5% significance and 80% power, a minimum of 30 patients will be needed in each study group. Baseline characteristics will be compared between the two groups using Chi square, *t* tests, and Mann-Whitney U tests as appropriate. All data will be analyzed according to the intention-to-treat principle. A *p* value of  $\leq 0.05$  will be considered statistically significant.

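### The CT pleural-volume change is read on the scan that permits tube removal, so for most patients it would largely track day-0 volume; the end scan and the analysis need defining.

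*Combined protocol and SAP*

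**What the plan says.** The list of secondary outcome measures includes "Change in pleural fluid volume on chest CT scan from randomization (day 0) to prior to chest tube removal", measured in ImageJ by a radiologist blinded to allocation. The images are not research scans: "Volume of pleural effusion will be obtained by examination of radiographic images obtained during the standard-of-care CT examination".

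The two treatment sections describe one follow-up CT, with the same trigger and consequence in each arm. In the control-arm section, "a chest CT without contrast will be performed when chest tube drainage is < 75 mLs". In the thoracoscopy section, "if there was no evidence of significant pleural effusion (<200 ml), the catheter will be removed"; the control-arm section sets the same 200 mL limit. The thoracoscopy section also describes the volume calculation: "The fluid volume will be calculated by measuring the maximum perpendicular distance between the surface and the chest wall".

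On patients who do not follow this path, the thoracoscopy section says "Any need for additional drainage or administration of fibrinolytic or surgery will be considered treatment failure". The control-arm section has a parallel sentence that also covers doses beyond six. Neither says which CT then supplies the outcome.

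The statistical section states "Baseline characteristics will be compared between the two groups using Chi square" along with t and Mann-Whitney tests, and "All data will be analyzed according to the intention-to-treat principle". It names no test or model for this outcome and no rule for missing data. Under Patient Population, a complicated parapneumonic effusion can qualify on ultrasound alone, so a day-0 CT is not assured.

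**The concern.** An outcome meant to show how completely each treatment clears the pleural space should be free to differ between arms at the end reading. Here the scan that supplies the end reading is also the scan that decides whether the tube comes out. Among patients removed under the rule, both arms are brought to roughly the same end range before the radiologist opens the images, and blinded reading cannot undo that. What still varies freely is the day-0 volume, which treatment cannot affect.

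Any contrast in residual fluid would then sit mainly with patients at 200 mL or more on the first low-drainage scan, and these are the patients for whom the documents name no scan. Two analysts could follow the text faithfully and use different readings. Tube days and failure rate already capture speed and the need for more treatment. This is the only listed outcome that measures clearance on imaging, so a null result could be misread as equal clearance.

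**Working it through.** **No plan figure to reproduce.** The documents give no standard deviation, effect size or power for this outcome. The 30 per arm was set for post-intervention stay and is used here only as the available number.

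**From the documents:** CT when drainage is below 75 mL; removal below 200 mL; same rule in both arms; 30 per arm.

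**Assumed, because the documents give no volumes:** day-0 SD (SDb) 150 to 400 mL; end volume under the rule uniform on 0 to 200 mL and independent of day 0.

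**Step 1. Share of the change-score variance due to day-0 volume.** The end-volume variance is 200²/12 = 3,333. The share is SDb²/(SDb² + 3,333).

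| SDb (mL) | Share | Chance difference in arm baseline means, 1.96 × SDb × √(2/30) |
|---|---|---|
| 150 | 22,500/25,833 = 87% | 76 mL |
| 200 | 40,000/43,333 = 92% | 101 mL |
| 300 | 90,000/93,333 = 96% | 152 mL |
| 400 | 160,000/163,333 = 98% | 202 mL |

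**Step 2. How much contrast the rule leaves.** Take first-CT volume as exponential with mean 150 mL in one arm and 300 mL in the other. The proportions at 200 mL or more are exp(−200/150) = 26% and exp(−200/300) = 51%. If everyone is eventually read below 200 mL, the arm means become 78 and 89 mL. A 150 mL difference shrinks to 11 mL. Using the Step 1 variances, the standard error of an unadjusted change difference is √[(SDb² + 3,333) × 2/30], which is 42 mL at SDb 150 and 104 mL at SDb 400. Without the day-0 term it is √(3,333 × 2/30) = 15 mL.

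**Step 3. Simulated power.** 10,000 runs, 30 per arm, two-sided 5%, normal baseline with mean 700 mL, latent correlation 0.3 with first-CT volume. Ranges are over SDb 150 to 400. Example: 150 v 300 mL.

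| How patients at 200 mL or more are read | Unadjusted change | Adjusted for day-0 volume |
|---|---|---|
| All later, below 200 mL | 5%–6% | 11% |
| Half later, half on first CT | 11%–27% | 36% |
| All on first CT | 28%–67% | 74% |

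Comparing first-CT volume with neither subtraction nor adjustment gives about 72%. With 20% of day-0 volumes mean-imputed, the adjusted first-CT figure is about 73%.

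**Step 4. Smaller effects.** For 150 v 225 mL, unadjusted change gives 5%–26% and adjusted first CT 32%–34%. For 150 v 200 mL, the figures are 5%–16% and about 19%.

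**Step 5. Null case.** With 200 v 200 mL, every analysis rejects in 4.6%–5.4% of runs, so none favours an arm.

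**The case against.** The strongest reply is that this is one item in a list of secondary outcomes with no power claimed for it, and that the statistical section names no test for any outcome, the primary included. The plan is silent on the model; it does not commit to an unadjusted change score. That stands, and it limits the severity. The outcome is nevertheless defined as a change, and nothing in the text leads an analyst to adjust it.

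Second, the natural meaning of a reading before tube removal is the last CT before removal, so reading everyone on the first CT is not the obvious interpretation. That is fair. But no repeat CT is described either, so the alternative is no better supported, and neither covers patients who leave the rule through surgery, another drain, rescue fibrinolytic or death.

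Third, the power figures rest wholly on assumed volumes, and at SDb 400 the normal baseline gives about 4% negative values. This also stands: the figures are illustrations. The structural point needs only the removal rule.

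Fourth, the day-0 covariate adds little once the first-CT volume is used (about 72% without it, 74% with it). Correct: most of the gain comes from not subtracting baseline and from using the first CT.

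A reader might infer that the outcome is biased towards one arm. The documents do not support that: trigger and threshold are the same in both arms, the reader is blinded, and the null simulation holds its level. Nor do they support a strict cap at 200 mL, because the treatment section works from a perpendicular distance and the outcome from ImageJ; a scan that met the rule could exceed 200 mL on the outcome measure.

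**Conclusion.** The concern holds in a limited form. For patients whose tube is removed under the rule, the end volume is roughly confined to 0 to 200 mL in both arms, and the change score mostly reflects day-0 volume (87% to 98% of its variance under the stated assumptions). That the outcome scan and the removal scan coincide follows from reading the sections together; no sentence says so outright. The documents leave open which CT counts for everyone else.

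The consequence is lost sensitivity and exposure to chance baseline imbalance in a single secondary outcome. The primary outcome and the sample size do not depend on it. It would be tempting to say the outcome has no power at all, since one reading gives 5% to 6%. That requires every patient at 200 mL or more to be rescanned below it, which the documents neither state nor schedule; other readings give up to 67% in the same example. This is worth considering and is best settled before unblinded data are seen, because choosing the scan afterwards would depend on the data.

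**What to change.** Change the analysis wording only. The scans, the blinded reader and the tube-removal rule stay as they are.

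1. Compare end ImageJ volume between arms by ANCOVA with day-0 CT volume as covariate, in place of an unadjusted change. Where the day-0 CT is missing, impute the overall mean, blind to arm.
2. Take the end reading from the first CT triggered by low drainage, whether or not the tube is then removed. Keep the pre-removal change now in the plan as a supporting summary, since this step alters the outcome's definition and should be presented as such.
3. Report the proportion not cleared (200 mL or more) on that CT. Count as not cleared anyone who, before it, died or met a treatment-failure criterion in the two treatment sections.
4. Do not enter volumes measured after rescue treatment or surgery in the ANCOVA as if they reflected assigned treatment. Report by arm how many patients have no eligible CT, and why.
5. Add a worst-rank sensitivity analysis in which only death or treatment failure takes the worst rank, not tubes lost or removed for other reasons. This sits alongside the plan's intention-to-treat statement, but patients with neither a CT nor a failure still have no value and must be shown.

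The cost is a few sentences and no extra scan. The downsides are real: the reading is unchanged for patients already below 200 mL on the first CT (74% and 49% in the 150 v 300 mL example), scan timing still depends on response, and power stays low for smaller effects.

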## **Sample Size and Statistical Analysis**

The difference in length of post-intervention hospital stay of 2 days between the two treatment arms would be clinically important.

This rationale was based on previous large VATS case series reported by Luh and colleagues in which the mean postoperative stay was  $7.2 \text{ d} \pm 3.2 \text{ d}$  versus  $11.8 \text{ d} \pm 9.4 \text{ d}$  from randomization to fibrinolytic therapy until discharge in the MIST2 trial and  $10 \text{ d} \pm 1.8 \text{ d}$  from first intrapleural treatment dose until discharge reported by Piccolo and colleagues.

To demonstrate this difference with 5% significance and 80% power, a minimum of 30 patients will be needed in each study group. Baseline characteristics will be compared between the two groups using Chi square, *t* tests, and Mann-Whitney U tests as appropriate. All data will be analyzed according to the intention-to-treat principle. A *p* value of  $\leq 0.05$  will be considered statistically significant.

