**Rationale:**

The intrapleural therapy of combined tissue plasminogen activator (tPA) and human recombinant deoxyribonuclease (DNase) in the management of pleural infection has been shown to improve the chest radiographic appearance at day 7 in the Multi-center Intra-pleural Sepsis Trial (MIST2). However, this approach is expensive, with a substantial hospital stay (around 12 days), and had a no significant decrease in the rate of surgery referral as compared to placebo.

Although two randomized studies have shown that around 80% of patients with pleural infection can be successfully managed medically, early surgical intervention is still considered a first-line treatment for pleural infection in some regions around the world. This approach has been justified on the basis of improved clinical outcome and shorter hospital stays for patients managed in this way.

Video-assisted thoracoscopic surgery (VATS) has been suggested as a surgical invasive approach to clear potentially infected material from the pleural space. In one small randomized and another non-randomized prospective trial comparing VATS with intercostal drainage plus intrapleural streptokinase, VATS was associated with decreased hospital stays and overall costs. However, there are several limitations that need to be mentioned. First, these two trials were under-powered studies without appropriate sample size calculation. Second, VATS was compared to intrapleural streptokinase. The intrapleural activity of endogenous plasminogen activator inhibitor (PAI-1) in the pathogenesis of pleural infection is important since this mediator not only directly inhibits streptokinase but has also been shown to contribute to the severity of loculation and poor outcomes with intrapleural fibrinolytic therapy. Third, large case series have shown that VATS is usually performed on a younger and less comorbid population (i.e. highly selected patients), compared to the unselected population of patients (which are usually sicker, elderly and have multiple comorbidities) with pleural infection seen in the fibrinolytic studies. Moreover, failure to respond to medical fibrinolytic therapy might

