## **Study Outcome**

### **Primary outcome measure:**

- Duration of hospital stay after intervention, as defined as thoracoscopy in the treatment arm and first dose of fibrinolytic in the control arm

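### Is the 80% power claim for 30 patients per group unsupported because no planning SD is named?

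*Combined protocol and SAP*

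**What the plan says.** The primary outcome is "Duration of hospital stay after intervention, as defined as thoracoscopy in the treatment arm and first dose of fibrinolytic in the control arm" (Primary outcome measure). The Sample Size and Statistical Analysis section calls a 2-day difference in this stay clinically important and then gives the size: "To demonstrate this difference with 5% significance and 80% power, a minimum of 30 patients will be needed in each study group". The Study Design section gives the matching total of 60.

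Between those two statements the sample size section cites three sources, opening with "This rationale was based on previous large VATS case series":

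- a surgical VATS series, 7.2 ± 3.2 d after operation;
- the randomized tPA/DNase trial, 11.8 ± 9.4 d, timed "from randomization to fibrinolytic therapy until discharge in the MIST2 trial";
- a tPA/DNase case series, 10 ± 1.8 d, timed "from first intrapleural treatment dose until discharge".

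None of the three spreads is identified as the planning SD. Sidedness is not given. The only tests named are for another purpose: "Baseline characteristics will be compared between the two groups using Chi square", followed by t and Mann-Whitney tests.

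**The concern.** A power statement for a difference in means has no content without an SD, and here the reader must guess it. The two control-arm spreads, for the same treatment, differ by a factor of about 5 (9.4 / 1.8 = 5.2). Depending on which one applies, the same 60 patients give a well-powered trial or one with little chance of detecting the difference the plan calls important.

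The thoracoscopy-arm value is also borrowed. The trial's procedure is medical thoracoscopy ("Patients will undergo medical thoracoscopy (rigid or semi-rigid) within 48 hours of randomization"), whereas 3.2 d comes from surgical VATS. The Rationale itself warns that "VATS is usually performed on a younger and less comorbid population (i.e. highly selected patients". The documents give no SD of stay for medical thoracoscopy. If the 80% rested on an unsuitable SD, the trial would be under-powered and its readers would not know.

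**Working it through.** **Inputs.** Difference d = 2 d, n = 30 per group, 5% significance, 80% power, and spreads of 3.2, 9.4 and 1.8 d, all from the sample size section. Assumptions: ± means SD, the test is a two-sided two-sample t-test, stay is roughly normal, and 3.2 d applies to the thoracoscopy arm.

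**Formulas.** Root-mean-square SD: s = √[(s₁² + s₂²)/2]. Normal-approximation size: n = 2(1.960 + 0.842)² s²/d² = 15.70 s²/d². Standard error at 30 per group: s√(2/30) = 0.2582 s. Power below is from the non-central t distribution with 58 df.

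**Reproducing the 30 (SDs 3.2 and 1.8).**
- s = √[(10.24 + 3.24)/2] = √6.74 = 2.596 d.
- n = 15.70 × 6.74/4 = 26.5, so 27; the t-test needs 28, and Mann-Whitney (by its asymptotic relative efficiency) 29.
- Standard error 0.670 d; d/SE = 2.98; power 83.5% (pooled t), 83.2% (Welch), 81.7% (Mann-Whitney, same approximation).

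By each of these methods 30 is enough for 80%.

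**Other control SDs beside 3.2 d.**

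| Control SD | s | d/SE | Power at 30 | n per group for 80% |
|---|---|---|---|---|
| 1.8 | 2.596 | 2.98 | 83.5% | 28 |
| 3.2 | 3.200 | 2.42 | 66.3% | 42 |
| 9.4 | 7.021 | 1.10 | 19.2% | 195 |

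**Room for error.** At 30 per group, 80% power for 2 d needs s ≤ 2.719 d.
- Beside 3.2 d, the control SD may be at most √(2 × 2.719² − 3.2²) = 2.13 d.
- Beside 1.8 d, the thoracoscopy SD may be at most √(2 × 2.719² − 1.8²) = 3.40 d.
- At SDs 3.2/9.4 the difference detectable with 80% power is 2 × 7.021/2.719, about 5.2 d.

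**Could another cited combination explain 30?** 3.2 d in both arms at one-sided 5% needs 33, and 30 then gives 77%, short of the claim. 3.2/9.4 is far off even one-sided (29% power). The section also speaks of a difference without a direction, which suits a two-sided test. Among these candidates, two-sided 3.2/1.8 is the only pair that lands near 30 and also reaches 80%.

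**Skewed stays.** With lognormal stays of mean 8 (SD 3.2) and 10 (SD 1.8), simulated power is 81% (t) and 93% (Mann-Whitney), so the claim survives. With means 9.8 (SD 3.2) and 11.8 (SD 9.4), it is 14% (t) and 6% (Mann-Whitney). The 6% says little about a 2-day difference, because the two medians in that model are 9.32 and 9.23 d and a rank test has almost nothing to find.

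**The case for a change.** The strongest case for a change runs as follows. The plan prints two control spreads for the same treatment and claims 80% without condition, although one of them gives about 19%. The 1.8 d comes from a case series and the 9.4 d from a randomized trial. The different starting point of the clock can hardly explain a five-fold difference in spread. Even on the favourable pair, the borrowed thoracoscopy SD has only 3.40 − 3.2 = 0.2 d of room. With observed SDs of 3.2 and 9.4, the 95% CI would have a half-width of 2.00 × 0.2582 × 7.021 = 3.6 d, so a non-significant result could not rule out 2 days in both directions. A sentence naming the SDs, sidedness and test would cost nothing.

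Most of this stands as a description of risk. The 80% is fragile, and the paragraph would be better with its inputs stated. It does not show that the stated figure is wrong. Nor does the argument from a null result carry over to the plan: the width of the interval depends on the SDs observed in the trial, not on the planning SD in the text, and nowhere does the plan say that it will read p > 0.05 as equal stay. Stating the inputs would disclose the risk, but without more patients it would not reduce it.

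**Conclusion.** The missing planning SD, sidedness and primary test are gaps in reporting, and a statistician can fill them from the same section. The cited pair 3.2/1.8 d with a two-sided 5% t-test needs 28 per group and gives about 83% power at 30. Its control value shares the primary outcome's starting point, which is a fair reason to prefer it to a value timed from randomization. For power on that pair, the choice between a t-test and Mann-Whitney hardly matters (28 against 29 per group).

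The documents do not confirm that this pair was the one used; it is an inference from the fit. The conclusion also rests on reading ± as SD and on accepting the VATS-series value for medical thoracoscopy. A reader of the trial should know that power would be about 19% at the MIST2 spread and should look at the confidence interval of the primary difference. A clearer sentence would be welcome, but neither the sample size nor the result depends on it, so no change to the plan is called for.

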**Methods and Procedures:**

**Study Design**

This prospective randomized trial will be conducted at UF Health Shands Hospital in accordance with Good Clinical Practice Standards and under IRB supervision. A large number of patients with pleural infection are treated at our institution, with a multidisciplinary team comprised of experienced interventional pulmonologists, chest radiologists and thoracic surgeons. We plan to enroll a total of 60 patients with pleural infection that will be randomized utilizing a computerized system to either medical thoracoscopy (thoracoscopy group) or fibrinolytic therapy (fibrinolytic group).

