**Patient Population**

Subjects (> 18 years of age) with either CPPE or empyema will be screened for inclusion.

Screening logs recording reasons for non-trial entry will be kept.

CPPE is defined as non-purulent effusion in a patient with clinical evidence of infection such as fever and/or elevated blood leukocyte count and/or elevated CRP, with pleural fluid pH  $\leq$  7.2 (measured by blood-gas analyzer), or pleural fluid glucose < 60 mg/dl or pleural fluid LDH >1000 IU/L. Empyema is defined as pus within the pleural space and/or presence of bacteria on pleural fluid Gram stain or culture.

For patients to be considered for the trial they need to fulfill one of the following criteria: 1) CPPE along with evidence of septated pleural effusion on pleural ultrasonography and/or chest CT scan (Figure 1) or 2) empyema.

[figure not shown]

Figure 1. Thoracic ultrasound showing complex pleural effusion along with septation (arrowhead)

Prescreening / Study exclusion criteria are as follows:

- 1) age <18 years;
- 2) pregnancy
- 3) inability to give informed written consent;
- 4) previous thoracic surgery or thrombolytic therapy for pleural infection;
- 5) medical thoracoscopy cannot be performed within 48 hours;

- 6) inability to tolerate procedure due to hemodynamic instability or severe hypoxemia;
- 7) inability to correct coagulopathy;
- 8) presence of a homogeneously echogenic effusion on pleural US (Figure 2).

[figure not shown]

Figure 2. Thoracic ultrasound showing homogeneously echogenic loculated effusion

Patients who agree to participate in the trial will sign an informed consent. Next, all patients will undergo diagnostic thoracentesis as per standard of care. In addition to standard of care testing on pleural fluid, an additional 10 mLs of fluid will be collected to check for markers like interleukin-8 and vascular endothelial growth factor. All patients will receive intravenous antibiotics according to local hospital guidelines and local microbiology results. Intravenous antibiotics will be changed to oral consolidation therapy by the managing consultant in light of the clinical response. Antibiotic therapy will be continued for between 2 and 6 weeks, as required per standard of care.

Following diagnostic thoracentesis and confirmation of pleural infection, participants will be randomly assigned to either receive thoracoscopy (treatment arm) or fibrinolytic therapy (control arm). (Figure 3)

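### No outcome model or baseline covariates are specified; pre-specified adjustment for day-0 values is a low-cost gain of uncertain size, clearest for CT fluid volume

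*Combined protocol and SAP*

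**What the plan says.** The whole analysis plan is the section Sample Size and Statistical Analysis. It states that "Baseline characteristics will be compared between the two groups using Chi square", t tests and Mann-Whitney tests as appropriate, then adds the intention-to-treat principle and a significance threshold. No method is attached to any outcome. No covariate, regression model or ANCOVA appears anywhere in the document. Study Design describes randomization only as computerized and mentions no stratification.

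Two secondary outcomes have a day-0 value of their own: "Change in pleural fluid volume on chest CT scan from randomization (day 0) to prior to chest tube removal" and "Infectious biomarker (CRP) from randomization (day 0), at removal of chest tube and 12 weeks as per standard of care". Patient Population sorts entrants into CPPE with septation or empyema ("For patients to be considered for the trial they need to fulfill one of the following criteria"), and age is part of eligibility. The Background reports higher mortality over age 65 and in immunocompromised patients. In both arms the Study Protocol removes the tube once CT shows less than 200 ml.

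The sample size rests on a difference in mean stay: "The difference in length of post-intervention hospital stay of 2 days between the two treatment arms would be clinically important". From this the plan concludes that "a minimum of 30 patients will be needed in each study group".

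**The concern.** A baseline significance test in a randomized trial asks only whether a chance difference is unusually large for chance. It does not remove the difference, and it invites covariates to be chosen after the data are seen. Naming a few covariates in advance avoids that choice, usually improves precision, and makes the estimate more accurate given the imbalance that actually occurred.

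For fluid volume the definition itself carries a cost. If follow-up volumes are held below 200 ml by the removal rule while day-0 volumes vary freely, the change score is mostly day-0 volume with its sign reversed. Chance differences in day-0 volume then pass almost directly into the treatment comparison.

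**Working it through.** **1. The plan's own figure.** Inputs from Sample Size and Statistical Analysis: difference 2 d, 5% significance (two-sided assumed), 80% power, 30 per arm. The SD used is not stated. The formula is n per arm = 2(1.960 + 0.842)² SD²/2² = 3.92 × SD².

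- SD 1.8 (tPA/DNase series): 12.7, so 13.
- SD 3.2 (VATS series): 40.2, so 41.
- SD 9.4 (MIST2): 346.8, so 347.
- Root mean square of 3.2 and 1.8, √((3.2² + 1.8²)/2) = 2.60: 26.5, so 27 (28 by the t-test).

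None of these gives 30 exactly. The SD at which 30 per arm has 80% t-test power for 2 d is 2.72.

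**2. Primary outcome.** Stay has no baseline value of its own, so any gain depends on the correlation r between the covariates together and stay. The documents give no r, and 0.2 to 0.5 is an assumption. For a linearly adjusted mean difference the residual SD is SD × √(1 − r²). Power is by two-sided t-test with 30 per arm, ignoring the few degrees of freedom spent on covariates.

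| r | variance removed (r²) | power, SD 2.72 | power, SD 3.2 | power, SD 9.4 |
|---|---|---|---|---|
| 0 | 0% | 80% | 66% | 13% |
| 0.2 | 4% | 82% | 68% | 13% |
| 0.3 | 9% | 84% | 70% | 14% |
| 0.5 | 25% | 90% | 78% | 15% |

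At SD 2.72 the standard error falls from 2.72 × √(2/30) = 0.70 d to 0.69 d at r = 0.2 and 0.61 d at r = 0.5.

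**3. Fluid volume.** Let k be the follow-up SD divided by the day-0 SD, and r the correlation between the two volumes. With the day-0 variance set to 1:

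- change-score variance = 1 + k² − 2rk;
- ANCOVA variance = k²(1 − r²);
- ratio of ANCOVA to change score = k²(1 − r²)/(1 + k² − 2rk).

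With equal variances (k = 1) the ratio is (1 + r)/2: 0.65 at r = 0.3 and 0.75 at r = 0.5. For k below 1 it is lower. The documents give no volumes. Taking k = 0.5 as an illustration, the ratio is 0.25 × 0.91/0.95 = 0.24 at r = 0.3 and 0.25 × 0.75/0.75 = 0.25 at r = 0.5.

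The correlation between day-0 volume and the fall in volume is (1 − rk)/√(1 + k² − 2rk). At k = 0.5 and r = 0.3 it is 0.85/√0.95 = 0.87. That is the sense in which the raw change is largely day-0 volume.

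**4. Chance imbalance.** With 30 per arm the standard error of a standardized baseline difference is √(2/30) = 0.26. The chance of a difference above 0.25 SD in a given covariate is about one in three, and above 0.5 SD about 5%. The chance that the empyema share differs by at least 20 percentage points (6 patients) is 19.6% if 30 of the 60 have empyema and 17.0% if 20 or 40 do (hypergeometric; the shares are assumptions).

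**The case against.** A reader might infer that the plan has chosen unadjusted analyses, or a raw-change analysis of fluid volume. It has not. It specifies no outcome analysis at all, which is the larger gap. The outcomes section defines a measure, and ANCOVA on the change gives the same treatment estimate as ANCOVA on the follow-up value, so the definition does not rule ANCOVA out. What stands is that nothing in the plan calls for adjustment.

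A reader might also infer that imbalance biases the comparison. Under randomization it neither biases an unadjusted test nor inflates its type I error. The cost is precision and accuracy conditional on the imbalance seen.

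Nor do the documents show that day-0 values exist for every patient. CRP and CT are obtained as standard of care, ultrasound can replace CT in showing septation, and empyema may be established by a culture that returns after treatment starts. The fix therefore needs a missing-covariate rule and an empyema classification fixed at randomization.

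The power gain in the primary outcome is conditional on an assumed r and an unstated SD. At r = 0.2 it is under two points, and the Background links age to mortality, not to stay. The 1 − r² formula also applies to a mean difference. It would not carry over to a proportional-odds model, which would leave the 2-day scale behind the sample size.

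These limits reduce the size of the point but do not remove it. Pre-specified adjustment with the unadjusted result alongside does not harm validity, and in large samples ANCOVA is at least as precise as a change score.

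**Conclusion.** The point holds in limited form. The plan has no outcome model and no pre-specified covariates, and its baseline tests do not correct chance imbalance in an unstratified 60-patient trial.

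The case is strongest for fluid volume. ANCOVA has (1 + r)/2 of the change-score variance if day-0 and follow-up variances are equal, and less if follow-up volume is the less variable, as the removal rule suggests.

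For the primary outcome the gain is plausible but its size is unknown: 4% to 25% of residual variance for an assumed correlation of 0.2 to 0.5. A reader might take adjustment as a remedy for low power. It is not one: at an SD of 9.4 d, power moves only from about 13% to 15%. Confidence is high that the specification is absent and moderate at best on how much adjustment would gain.

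**What to change.** In Sample Size and Statistical Analysis, state:

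1. Pre-removal CT fluid volume is analysed by ANCOVA with day-0 volume as covariate.
2. Log CRP at tube removal and at 12 weeks is analysed with day-0 log CRP as covariate.
3. The primary effect is the difference in mean post-intervention stay in days, the scale used for the sample size. It is adjusted for a short list known at randomization, for example age, empyema versus CPPE as classified at randomization, and day-0 log CRP. Robust or bootstrap standard errors allow for skew, and the unadjusted result is also shown.
4. Patients with a missing day-0 covariate stay in the analysis through simple imputation from baseline data alone.

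Baseline characteristics are better shown in a descriptive table than tested.

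The cost is wording, agreed before outcome data are seen. No extra patients or procedures and no change to randomization are needed. The small downside is the handling of missing day-0 values.
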